10.2.6 Adverse Events

Study personnel must remain vigilant for the occurrence of AEs, particularly those that may be life-threatening. Personnel who are trained in the acute management of anaphylaxis and other emergencies and who have access to appropriate clinical supplies must be immediately available for 30 minutes after dosing. Treatment of SAEs should be primarily supportive of vital functions.

AE Definition: An AE is defined as any untoward medical occurrence in a patient or clinical investigation patient who had received an administration of a pharmaceutical product; the occurrence does not necessarily have to have a causal relationship with this treatment. An AE can therefore be any unfavorable and unintended sign (including an abnormal laboratory finding), symptom, or disease temporally associated with the use of Visipaque™ or saline,

whether or not considered related to that product. Only symptoms/signs that begin or worsen in severity and/or frequency after signing informed consent will be recorded as AEs in the eCRF.

The patients will be closely observed and questioned for any kind of AE during the study procedures and at follow-up appointments throughout the study period with non-leading questioning (e.g., “How do you feel?”). The patients will be instructed to immediately report any symptoms and signs to the study staff (i.e., between formal observations). AEs and SAEs will be recorded from time of signing informed consent until Follow-up 3.

Both the Investigator(s) and Sponsor/CRO will perform a causality assessment on any AE, to assess whether or not there is a reasonable possibility (evidence to suggest) that Visipaque™ or saline caused the event.

Causal relationship

The relationship of an AE with Visipaque™ or saline will be assessed and reported by the investigator as:

- Reasonably related to study drug (“Reasonable cause”): - A causal relationship between Visipaque™ or saline and an AE is at least a reasonable possibility, i.e., the relationship cannot be ruled out.
- Not reasonably related to study drug (“Not reasonable cause”): - A causal relationship between Visipaque™ or saline and an AE is not a reasonable possibility.

A suspected adverse reaction is an AE where reasonable possibility exists for causality between Visipaque™ or saline and the AE.

Expectedness

All Visipaque™-emergent AEs will be assessed, by the Sponsor/CRO, as to whether they were expected to occur or unexpected, meaning not anticipated based on current knowledge found in the applicable safety information included in the IB for Visipaque™.

Unexpected: An unexpected Visipaque™-emergent AE is a reaction, for which the nature, seriousness, severity or outcome is not consistent with the applicable safety information included in the IB.

Expected: An expected Visipaque™-emergent AE is a reaction which is consistent with the applicable safety information included in the IB.

Laboratory AE Evaluation

Interpretation and follow-up of abnormal laboratory test results should be conducted in consideration of the clinical situation of the patient. Any abnormal laboratory findings that constitute an AE should be reported as such and should be followed up until the outcome is known. Also, additional diagnostic tests may be indicated to determine a more precise diagnosis of the patient’s condition (e.g., ordering a WBC differential to help characterize a

high or low WBC count, or ordering a determination of red cell indices to help characterize a low hematocrit).

To ensure a consistent approach, an AE/SAE should always be reported in the CRF for AKI if laboratory test results show a SCr increase of ≥ 0.3 mg/dL (≥ 26.4 μ mol/L) or an increase to $\geq 150\%$ to 200% (≥ 1.5 to 2.0 fold) from baseline and/or the previous test result.

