7.2 Inclusion Criteria

Patients may be included in the study if they meet all of the following criteria:

- (1) Is ≥ 18 years of age at the time that written informed consent is obtained.
- (2) Is male or is a non-pregnant, non-lactating female who is either surgically sterile (has a documented bilateral tubal ligation or oophorectomy and/or documented hysterectomy) or is postmenopausal (cessation of menses for more than 1 year). Women of childbearing potential must use adequate contraception* from Screening until 30 days after the Baseline Visit and must have a negative result for a urine human chorionic gonadotropin pregnancy test at the Baseline Visit.
- (3) Is an outpatient who has undergone successful EVAR and is scheduled for his/her next post-procedural imaging follow-up examination.
- (4) Has previously completed one or more of his or her post-EVAR surveillance imaging examination(s) that provided evidence on stable post-EVAR status.
- (5) Has a documented diagnosis of stage III or IV (defined as $30 \leq$ estimated glomerular filtration rate (eGFR) <60 mL/min/1.73 m² and $15 \leq$ eGFR <30 mL/min/1.73 m², respectively, according to the Modification of Diet in Renal Disease [MDRD] equation) CKD and stable renal function (last 2 SCr values within ± 0.5 mg/dL of each other, with the most recent value within 14 days prior to the scheduled CT examination and the preceding value within 1 to 12 months before that).
- (6) Is able to provide written informed consent.
- (7) Is able and willing to comply with all study procedures as described in the protocol.

* Adequate contraception is based on those methods identified in the Clinical Trial Facilitation Group (CTFG) document [[CTFG Guidance 2014](#)] for clarification of effective contraception. Such methods include: combined (estrogen- and progestogen-containing) hormonal contraception associated with inhibition of ovulation (oral, intravaginal, or transdermal); progestogen-only hormonal contraception associated with inhibition of ovulation (oral, injectable, or implantable); intrauterine device; intrauterine hormone-releasing system; bilateral tubal occlusion; vasectomized partner; sexual abstinence, progestogen-only oral hormonal contraception, where inhibition of ovulation is not the

primary mode of action, male or female condom with or without spermicide cap, diaphragm or sponge with spermicide (refer to Section 8.6).

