10 EFFICACY, SAFETY, AND OTHER VARIABLES

10.1 Endpoints

10.1.1 Primary Endpoint

Incidence of AKI stage ≥ 1 (AKIN SCr criteria) following an i.v. injection of iodinated iso-osmolar contrast material iodixanol (VisipaqueTM Injection 320 mgI/mL) or saline in patients with CKD stage III/IV assessed at 48 hours post-baseline (Follow-up 1).

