10.2.1 Clinical Laboratory Evaluation

Clinical laboratory parameters assessed in this study are displayed in [Table 2](#). Local laboratories will be used for measuring screening parameters. A central laboratory will be used for analysis of SCr, cystatin C, and N-GAL biomarkers at Baseline, Follow-Up 1, Follow-Up 2 (if a clinic visit takes place), and Follow-Up 3 (SCr only).

Table 2 Clinical Laboratory Parameters

Screening	Baseline	Baseline 4 hours post scan	Follow-Up 1 (48 hours \pm 6 hours)	Follow-Up 2 (7 days \pm 2 days)	Follow-Up 3 (6 months \pm 2 weeks)

Local Laboratory:
 
Clinical Chemistry:
 
Chloride
 
Urea nitrogen
 
Serum creatinine
 
Bicarbonate
 
Sodium
 
Potassium
 
Glucose
 
Alkaline phosphatase
 
Aspartate transaminase
 
Alanine transaminase
 
Bilirubin (Total)
 
Thyroid-stimulating hormone (TSH)^a
 
Hematology:
 
Hematocrit
 
Hemoglobin
 
Platelet count
 
White blood cell (WBC) count
 
Lymphocyte %
 
Urinalysis (local lab):
 
Glucose
 
Ketone
 
Protein
 
Blood
 
Pregnancy Test:
 
Urine dipstick
	
Central Laboratory:
 
Clinical Chemistry:
 
Serum creatinine
 
Cystatin C
 
Neutrophil gelatinase-associated lipocalin (N-GAL)
 
Local Laboratory:
 
Urinalysis:
 
NephroCheck® biomarkers (TIMP-2, IGFBP-7)^b
 
Local Laboratory:
 
Urinalysis:
 
NephroCheck® biomarkers (TIMP-2, IGFBP-7)^b
 
Pregnancy Test:
 
Urine dipstick
	
Local Laboratory:
 
Urinalysis:
 
NephroCheck® biomarkers (TIMP-2, IGFBP-7)^b
	
Central Laboratory:
 
Clinical Chemistry:
 
Serum creatinine
 
Cystatin C
 
N-GAL
 
Local Laboratory:
 
Urinalysis:
 
NephroCheck® biomarkers (TIMP-2, IGFBP-7)^b
	
Central Laboratory:
 
Clinical Chemistry:
 
For patients having met the primary AKI criteria:
 
Serum creatinine
 
Cystatin C
 
N-GAL
	
Central Laboratory:
 
Clinical Chemistry:
 
Serum creatinine

a supersensitive TSH (sTSH) assay if locally available

b If local testing is available

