12.2 Definitions

CKD staging [National Kidney Foundation 2002] [Kirsztajn 2009]:

Stage I: kidney damage with normal or high GFR (≥ 90 mL/min/1.73 m²)

Stage II: kidney damage with mildly decreased GFR (60-89 mL/min/1.73 m²)

Stage IIIA: moderately reduced kidney function (GFR 45-59 mL/min/1.73 m²)

Stage IIIB: moderately reduced kidney function (GFR 30-44 mL/min/1.73 m²)

Stage IV: severely reduced kidney function (GFR 15-29 mL/min/1.73 m²)

Stage V: very severe or end-stage kidney failure (GFR <15 mL/min/1.73 m²)

AKIN Serum Creatinine Criteria for AKI [AKIN 2015] [Mehta et al. 2007]:

Stage 1: a SCr increase of ≥ 0.3 mg/dL (≥ 26.4 µmol/L) or increase to $\geq 150\%$ to 200% (≥ 1.5 - to 2.0-fold) from baseline within 48 hours

Stage 2: a SCr increase to >200% to 300% (>2.0- to 3-fold) from baseline within 48 hours

Stage 3: a SCr increase to >300% (>3.0-fold) from baseline or SCr \geq 4.0 mg/dL (\geq 354 μ mol/L) with an acute increase of \geq 0.5 mg/dL (\geq 44 μ mol/L) within 48 hours

Standard definition of CIN [[Mehran and Nikolsky 2006](#)]:

Increase in SCr of 0.5 mg/dL or more in the 24 to 72 hours after the CT scan.

Waikar's definitions of AKI [[Waikar and Bonventre 2009](#)]:

Stage 1: 0.3 mg/dL increase in SCr over 24 hours or a 0.5 mg/dL increase in SCr over 48 hours

Stage 2: 0.5 mg/dL increase in SCr over 24 hours or a 1.0 mg/dL increase in SCr over 48 hours

Stage 3: 1.0 mg/dL increase in SCr over 24 hours or a 1.5 mg/dL increase in SCr over 48 hours.

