12.7.3.4 Adverse Events

AEs and SAEs will be coded using MedDRA and all reported events will be listed for the safety population. Treatment-emergent AEs are defined as AEs that occur from the time of treatment administration through Follow-Up 3. The number and percentage of patients with 1 or more AEs will be summarized by system organ class and preferred term overall and by treatment group (CECT vs NECT). Summaries will also be presented by AE intensity and judged relationship to Visipaque™ or saline placebo. Treatment-emergent SAEs are defined as SAEs that occur from the time of treatment administration through Follow-Up 3. Treatment-emergent SAEs will be presented by treatment group for the safety population.

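### The mandatory AKI adverse-event rule has no time limit, so six-month creatinine changes can be tabulated as treatment-emergent AKI alongside true 48-hour events

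*Combined protocol and SAP*

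**What the plan says.** Section 10.2.6 (Laboratory AE Evaluation) states that "an AE/SAE should always be reported in the CRF for AKI if laboratory test results show a SCr increase of" at least 0.3 mg/dL, or a rise to 1.5-fold or more, "from baseline and/or the previous test result". It sets no interval between the two samples.

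Section 12.2 gives the AKIN stage 1 definition with the same two thresholds, but the rise must occur "from baseline within 48 hours". The primary endpoint (10.1.1) and the three AKI secondary endpoints (10.1.2) are assessed at Follow-up 1, the 48-hour visit.

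Section 10.2.6 also says that "AEs and SAEs will be recorded from time of signing informed consent until Follow-up 3". Sections 9.5 and 10.2.1 schedule a central-laboratory creatinine for all patients at Follow-up 3, six months after baseline. Section 9.4 schedules a day-7 creatinine only for patients who met the AKI criteria at Follow-up 1.

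Section 12.7.3.4 states: "Treatment-emergent AEs are defined as AEs that occur from the time of treatment administration through Follow-Up 3". It tabulates AEs by system organ class, preferred term, arm, intensity and relationship. It plans no split by time of onset.

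Inclusion criterion 5 (7.2) accepts as stable two creatinine values within 0.5 mg/dL of each other, the latest within 14 days of the scan "and the preceding value within 1 to 12 months before that".

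**The concern.** The AE rule borrows the AKI thresholds and the AKI name but not the time limit that makes a rise acute. For most patients the scheduled test before Follow-up 3 is the 48-hour sample, taken about six months earlier and after the required fluid intake. A patient who dips at 48 hours and then returns close to baseline can therefore trigger a mandatory AKI report.

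What is at stake is how the safety tables read. Renal safety is the purpose of the trial, and readers will look for AKI in the AE table. If early events and six-month creatinine changes share one row, that row does not match the trial's own AKI definition, and an early difference between arms is harder to see.

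**Working it through.** **Scope of the rule.** Side by side:

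| | Section 12.2 (AKIN) | Section 10.2.6 (AE rule) |
|---|---|---|
| Threshold | 0.3 mg/dL or 1.5-fold | 0.3 mg/dL or 1.5-fold |
| Comparator | baseline | baseline and/or previous test |
| Window | 48 hours | none; AEs run to Follow-up 3 |

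For any comparator value of 0.6 mg/dL or more, a 1.5-fold value is a rise of at least 0.5 × 0.6 = 0.3 mg/dL. The 0.3 mg/dL limb therefore decides.

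**Single-patient example (illustrative values).** Baseline 2.0, 48 hours 1.8, six months 2.1 mg/dL. Against baseline, 2.1 − 2.0 = 0.1, so no trigger. Against the previous test, 2.1 − 1.8 = 0.3, so an AKI report is mandatory.

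**Plan figures.** The plan gives no expected number of AKI AEs. Its 10% AKI rate per arm (12.8) is for the 48-hour endpoint. The sample size built on it reproduces (exact power of the score test at 582 per arm is 80.5%) and is untouched by the AE rule.

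**How often, on assumptions.** The documents give no creatinine distribution, within-person CV or drift. Assume baseline, 48-hour and six-month values B, F1 and F3 are independent normal around a true level S, each with SD = CV × S. Add a drift d to F3, and assume no contrast effect and no true acute injury. Then:

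- Early flag: F1 − B ≥ 0.3, with probability 1 − Φ(0.3 / (CV × S × √2)). At S = 2.0 and CV 10% this is 1 − Φ(0.3 / 0.283) = 14.4%. At CV 7.5% it is 1 − Φ(0.3 / 0.212) = 7.9%.
- Late-only flag: (F3 − B ≥ 0.3 or F3 − F1 ≥ 0.3) and no early flag, obtained by simulation.

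Late-only flags as a share of all patients (a joint probability, not conditional on having no early flag):

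| True SCr (mg/dL) | CV | d = 0 | d = 0.1 mg/dL |
|---|---|---|---|
| 1.2 | 5% | under 0.1% | 1.7% |
| 1.2 | 10% | 6.0% | 17.9% |
| 1.5 | 5% | 0.4% | 5.3% |
| 1.5 | 10% | 11.1% | 23.6% |
| 2.0 | 5% | 2.9% | 12.7% |
| 2.0 | 7.5% | 11.1% | 23.7% |
| 2.0 | 10% | 18.0% | 28.9% |

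In 1164 patients this runs from about one or none (1164 × 0.001 = 1.2 as an upper bound) to about 336 (1164 × 0.289). With no drift, about half of the late-only flags come solely from the previous-test comparator.

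**What dilution means.** Suppose early AKI AE rates were 12% and 8% (illustrative). Take the S = 2.0, CV 7.5%, no-drift row, where the late-only share among patients without an early flag is 11.1 / (100 − 7.9) = 12%. The AE row would show 12 + 0.12 × 88 = 22.6% and 8 + 0.12 × 92 = 19.0%. The ratio falls from 1.5 to 1.19 and the difference from 4.0 to about 3.5 points.

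**The case against.** The strongest defence is that the two sections do different jobs. Section 12.2 defines the analysis endpoint. Section 10.2.6 is a capture trigger, applied alike in both arms, for events that need no causal link to treatment. A wide mechanical trigger is defensible in an open-label trial because it leaves less room for arm-aware discretion, and six-month follow-up exists to find late effects. This stands, and it is why the trigger should not be narrowed.

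There are also partial safeguards. Causality is assessed by investigator and sponsor, the tables split by intensity and relationship, laboratory changes are summarized at each time point (12.7.3.1), and the saline arm shows the background rate. None of these separates early from late AKI in the AE table. The instruction in 10.2.6 to interpret laboratory results in clinical context does not help either, because the AKI rule says reports are always made.

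A reader might infer more than the documents support:

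- *The tested endpoints are contaminated.* They use central creatinine at 48 hours, not AE terms.
- *AKI AEs become critical events.* Section 10.2.5 expects a critical event to have an associated AE. It does not say the reverse, and it notes that the terms can differ.
- *The blinded sample size re-estimation absorbs late events.* Section 12.8 uses the AKI rate as determined by the adjudication committee. The document does not say which definition the committee applies, so this cannot be concluded.
- *Screening-to-baseline rises count too.* They would be pre-treatment AEs (9.2), outside the treatment-emergent window.
- *Criterion 5 contradicts the rule.* It is an eligibility test and may use another threshold. It shows only that the protocol regards changes of this size over months as compatible with stable function.

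**Conclusion.** The mismatch in wording is certain: same thresholds and same name, no window, and an extra comparator. Followed literally, the rule lets six-month creatinine changes be counted as treatment-emergent AKI in descriptive tables that do not separate them from 48-hour events. The primary and AKI secondary analyses and the sample size are unaffected, so the point is minor.

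The size is not established. The range from under 0.1% to about 29% of patients depends wholly on the assumed creatinine level, CV and drift. The upper end should not be read as a forecast. At SCr 2.0 mg/dL and CV 10%, noise alone gives 14.4% AKI at 48 hours, above the 10% the trial planned for in total. It would also be wrong to set late flags as false against a true 10%, since the protocol does not call its planning rate free of measurement variation. The claim that the AKI AE rate will be dominated by CKD progression and noise is therefore not supported. Only the direction is: the rule can add late events to both arms and shrink an early contrast.

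**What to change.** Keep the reporting trigger in 10.2.6 as it stands, so that late rises are still captured without added discretion. Then make two changes.

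1. In 12.7.3.4, add a table by arm that separates (a) AKI AEs meeting the protocol's own definition, that is, a rise at Follow-up 1 against the central baseline value, from (b) creatinine-triggered AKI AEs with later onset. Within (b), show those triggered only by the Follow-up 3 sample and those triggered only by the previous-test comparator. Label (b) as late creatinine increase rather than AKI. Late AKI that rests on a clinical diagnosis should keep its AKI term in a row of its own.
2. Reconcile 10.2.6 with 12.2 by stating that the AE trigger is deliberately wider than the endpoint definition and that the two will be reported separately.

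The cost is one extra AE table and a derived flag for onset and comparator. The flag can be built from AE onset dates and the scheduled central creatinine values, so it also works for data already collected. No change to sample size, endpoints or site procedures is needed.

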10.2.7 Serious Adverse Events

An SAE is defined as any AE that:

- Results in death.
- Is life-threatening.
- Requires in-patient hospitalization or prolongation of existing hospitalization.
Hospitalizations that are not due to, or associated with, an AE should not be reported as an SAE, e.g., pre-planned hospitalizations for diagnostic tests.
- Results in persistent or significant disability or incapacity.
- Is a congenital anomaly or birth defect.
- Is another important medical event*.

(*Other important medical events are those that may not result in death, be life-threatening, or require hospitalization, but may be considered an SAE when, according to appropriate medical judgment, they may jeopardize the patient and may require medical intervention to prevent one of the outcomes listed above).

10.2.8 Other Significant Adverse Events

Clinical laboratory abnormalities that qualify as AEs (other than those meeting the definition for serious) and any events that lead to an intervention (including premature discontinuation of VisipaqueTM or saline, dose reduction or significant additional concomitant therapy), other than those reported as SAEs, will be reported and evaluated as other significant AEs.

10.2.9 Adverse Event and Serious Adverse Event Reporting

All AEs should be recorded from time of signing informed consent to the completion of Follow Up 3; acceptable diagnoses should be used, if possible. If an AE has already been reported, it is not necessary to report each individual sign and symptom of that AE as a separate AE. For example, if myocardial infarction is reported as an AE, there is no need to report elevated creatine kinase and abnormal ECG, or other related signs, symptoms, or laboratory values as separate AEs. However, if both occurred in isolation and myocardial infarction was not diagnosed, then each event would be reported as an AE.

The intensity of all AEs will be graded as mild, moderate, or severe using the following definitions:

Mild:	Tolerable.
Moderate:	Interferes with normal activity.
Severe:	Incapacitating (causes inability to perform usual activity or work)

The Investigator will be instructed to closely monitor each patient who experiences an AE (whether ascribed to Visipaque™ or saline or not) until the outcome of the AE has been determined.

In addition to the Investigator's own description of the AEs, each AE will be encoded by the Sponsor/CRO according to a well-recognized dictionary of medical codes.

All serious and non-serious AEs must be followed for a final outcome until the end of the follow-up period. An outcome of "unknown" is not considered to be an acceptable final outcome. An outcome of "not yet resolved" is an acceptable final outcome for non-serious AEs at the end of a patient's participation in a study, and for SAEs at database lock.

SAEs will be recorded in the eCRF if they occur as follows:

- After a patient first receives Visipaque™ or saline and throughout the patient's follow-up period,* whether or not considered related to Visipaque™ or saline, and
- After the patient's follow-up period, and for which a causal relationship to Visipaque™ or saline cannot be ruled out.

(*Follow-up period is defined as 6 months for SAEs and critical events reported for the purposes of adjudication or, for patients prematurely withdrawn from a study, the duration of a patient's participation.)

Investigators must report all SAEs to the Sponsor/CRO within 24 hours.

Details regarding how to notify the Sponsor/CRO of SAEs and contact details for any protocol or safety-related questions will be provided in a separate document.

The Sponsor/CRO (on behalf of the Sponsor) will report all SAEs to local health authorities, Independent Ethics Committees (IECs)/Independent Review Boards (IRBs) and Investigators as required by local regulations and Sponsor/CRO SOPs.

Patients enrolled at sites in the European Union will be provided with a Clinical Trial Participant card at the time of Visipaque™ or saline administration. This card will list contact details for the Investigator and for GE Healthcare medical emergency cover services (Clinical Trial Emergency Contact Service [CTECS]). The CTECS provides 24-hour, 7 day a week emergency cover service for healthcare professionals to seek advice on trial-related medical questions or problems should a medical emergency arise and the Investigator is not available.

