There is no universally accepted imaging protocol for post-EVAR surveillance (e.g., for detection of endoleaks, detection of mechanical changes in the stent-graft, and evidence of expansion or shrinkage of the residual sac). The American College of Radiology notes that computed tomography angiography (CTA) is considered the gold standard for the diagnosis of endoleaks [ACR 2012]. In 2010, the Society of Interventional Radiology published clinical practice guidelines for EVAR [Walker et al 2010]. These guidelines, which were endorsed by the Cardiovascular and Interventional Radiological Society of Europe and the Canadian Interventional Radiology Association, indicated that even though CTA is the most commonly used examination for post-EVAR surveillance, unenhanced CT, magnetic resonance angiography, ultrasonography, and even simple radiography, remain commonly used and appropriate. The recent ESC 2014 Guideline on the diagnosis and treatment of aortic diseases is also largely in line with guidelines published earlier in terms of imaging follow-up recommendations, and the use of color-Doppler US can be considered as an alternative in case neither endoleak nor abdominal aortic aneurysm sac enlargement was documented during the first year after EVAR [ESC Guidelines 2014]. In practice, vascular surgeons do not always

follow these guidelines; and if the results of the first post-EVAR CTA are negative, unenhanced CT or ultrasonographic exams are often ordered instead of CTA for continued surveillance. Thus, after the first post-EVAR examination, there is clinical equipoise between imaging methods that do and do not require administration of contrast medium. As a result, it is ethically acceptable to use randomization to assign some patients to receive contrast medium and some patients to be evaluated without the use of contrast medium.

This study's safety monitoring plan is justifiable and adequate from a safety standpoint in view of the following:

- The design of the safety plan permits a comparison of the safety response to Visipaque™ 320mg I/mL Injection compared to placebo (including non-contrast duplex ultrasonography) under baseline and post-investigational medicinal product (IMP) administration conditions.
- The 6-month safety monitoring follow-up permits the evaluation of late-appearing significant adverse effects that may emerge or progress after the administration of Visipaque™ 320mg I/mL Injection compared to placebo.

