7.4 Withdrawal and Termination Criteria

7.4.1 Patient Withdrawal

There are no formal withdrawal criteria for this study. During the conduct of the study, the Sponsor will review the safety data for trends and signals that would indicate the need for withdrawal of a patient.

In accordance with the Declaration of Helsinki, each patient is free to withdraw from the study at any time. Investigator(s) also have the right to withdraw patients from the study in the event of illness, AEs, or other reasons concerning the health or well-being of the patient, or in the case of lack of co-operation.

Should a patient decide to withdraw after administration of Visipaque™ 320 mg I/mL Injection or saline placebo, or should the Investigator(s) decide to withdraw the patient, all efforts will be made to complete and report the observations up to the time of withdrawal as thoroughly as possible. A complete final evaluation at the time of the patient's withdrawal should be made and an explanation given of why the patient is withdrawing or being withdrawn from the study.

The reason for withdrawal must be noted in the electronic Case Report Form (eCRF). If the reason for withdrawal is a clinical AE, monitoring will continue until the outcome is evident. The specific event or test result(s) must be recorded in the eCRF.

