12.6.3 Handling of Missing Values/Censoring/Discontinuations

Missing values will not be imputed, and only observed values will be used in data analyses and reports, unless otherwise specified in the Statistical Analysis Plan (SAP).

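### After withdrawal, SAE and critical-event collection shrinks to two narrow exceptions, which conflicts with the 6-month window and can bias the 6-month noninferiority comparisons if withdrawal differs by arm

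*Combined protocol and SAP*

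**What the plan says.** **Withdrawal (Section 7.4.1).** The section states "There are no formal withdrawal criteria for this study", but "Investigator(s) also have the right to withdraw patients from the study in the event of illness, AEs, or other reasons" touching the patient's health, or for lack of co-operation. After dosing, the site is to "complete and report the observations up to the time of withdrawal as thoroughly as possible" and make a final evaluation. One continuation is specified: "If the reason for withdrawal is a clinical AE, monitoring will continue until the outcome is evident".

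**Follow-up period (Section 10.2.9).** SAEs are recorded through a follow-up period of 6 months for SAEs and adjudicated critical events or, "for patients prematurely withdrawn from a study, the duration of a patient's participation". SAEs after that period are still recorded if a causal relationship to the study product cannot be ruled out.

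**Competing statements.** Table 1, footnote h, has critical events collected from administration to about 6 months, with no exception for withdrawn patients. Section 6.3 defends the safety plan on the ground that "The 6-month safety monitoring follow-up permits the evaluation of late-appearing significant adverse effects".

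**Analysis.** Section 12.7.1 lists all-cause death, critical events, hospitalization for renal failure, renal replacement therapy (RRT) and a composite at 6 months. The binary outcomes are tested with the same noninferiority method as the primary endpoint, in the safety population. Under Section 12.6.3 nothing is imputed and "only observed values will be used in data analyses and reports", unless the SAP says otherwise; Section 12.9 is similar. Section 8.4 says the study is not blinded.

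**The concern.** The study product is one injection. Once it has been given, withdrawal stops no study drug; it ends study procedures and observation. The plan therefore lets follow-up end because of illness or an AE, in patients who may well be at higher risk of a later event, and then no longer requires most of their later outcomes to be collected.

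Staff know the arm. If AEs lead to more withdrawals after contrast than after saline, more later events go unrecorded in the CECT arm, and the observed difference moves toward noninferiority. The endpoints exposed are the 6-month mortality and morbidity outcomes, which carry the long-term safety claim. Events that were never collected cannot be recovered at the analysis stage.

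**Working it through.** **1. The plan's own figure.** Section 12.8 assumes 10% in each arm, a margin of 5 points, one-sided 0.025, 80% power and the score test. The restricted estimates at the margin are 0.1303 and 0.0803, so

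n = [1.960·√(0.1303·0.8697 + 0.0803·0.9197) + 0.842·√(2·0.10·0.90)]² / 0.05² = 580.7, or 581 per arm.

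The plan states 582. Exact enumeration of the Miettinen-Nurminen test at 582 gives power 0.805. The figure reproduces and is not in question here.

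**2. What is collected after withdrawal.**

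| Event after withdrawal | Section 7.4.1 | Section 10.2.9 | Table 1, footnote h |
|---|---|---|---|
| Progression of the AE that caused withdrawal | Followed to outcome | Recorded if an SAE and causality not ruled out | Collected if a critical event |
| New SAE, causality not ruled out | Not required | Recorded | Collected if a critical event |
| New death, renal admission, RRT or EVAR-related event judged unrelated to the product | Not required | Not required | Collected to about 6 months |

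The third row is the gap. Section 10.2.9 and footnote h give different answers there. Which row a new event falls into depends on a causality judgement made by someone who knows the arm, whereas all-cause death and RRT are endpoints whatever their cause.

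**3. Size.** The documents give no withdrawal rate and no 6-month event rate, so all counts below are assumptions, with 582 per arm. The upper limit is the value d above the observed difference that solves

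(p1 − p2 − d) / √{[q1(1−q1)/n1 + q2(1−q2)/n2]·N/(N−1)} = −1.96,

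where q1 and q2 are the restricted estimates with q1 − q2 = d, and N = n1 + n2.

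*A few events lost (3 CECT, 1 NECT), patients kept as non-events:*

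| Full ascertainment | Upper limit | After loss | Upper limit |
|---|---|---|---|
| 41 vs 27 | 5.20% (fails) | 38 vs 26 | 4.78% (passes) |
| 44 vs 27 | 5.77% (fails) | 41 vs 26 | 5.36% (fails) |
| 36 vs 27 | 4.24% (passes) | not needed | – |

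*Withdrawal modelled directly.* True events are 34 vs 17 (5.8% vs 2.9%), upper limit 5.41%, fails. Suppose 30% to 50% of withdrawn patients have a later event that is lost:

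| Withdrawn, CECT vs NECT | Counted as non-events | Counted as missing |
|---|---|---|
| 12 vs 12 | 5.25% to 5.17% | 5.36% to 5.27% |
| 12 vs 6 | 4.94% to 4.70% | 5.07% to 4.82% |
| 17 vs 6 | 4.74% to 4.31% | 4.93% to 4.47% |

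Equal withdrawal of about 2% moves the limit by 0.05 to 0.24 points (5.41 − 5.36 and 5.41 − 5.17) and does not change the result. Withdrawal of 12 vs 6 changes it in three of four cases. Starting from 29 vs 12 (5.21%), even equal withdrawal of 12 per arm crosses in one of four cases (4.94%; 50% risk, counted as non-events), because that start lies only 0.21 points above the margin.

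*Low rates.* With 12 vs 6 events the limit is 2.66%, and with 18 vs 6 it is 3.92%. Both pass with full ascertainment, so lost events change no conclusion.

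**The case against.** A reader might infer that all collection stops at withdrawal. It does not. Section 7.4.1 keeps following the AE that caused withdrawal, and Section 10.2.9 keeps recording later SAEs whose causal link cannot be ruled out. A patient withdrawn for AKI who later starts dialysis is therefore not a sound example of a lost event: dialysis is part of that AKI's outcome, and causality after contrast would be hard to exclude. This stands, and it narrows the gap to later events judged unrelated.

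A reader might also infer that withdrawn patients are counted as non-events. The documents do not say whether they are non-events, missing or censored, and the missing-data rule yields to a SAP whose text on this point is not among the documents. That stands too, although a SAP rule could only set how such patients are counted; it could not supply the events.

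Third, no arm difference in withdrawal is documented, and the illustrations that change a result start close to the margin. Patients with AKI are called back for an extra clinic visit at day 7 (Section 9.4), and AKI must be reported as an AE or SAE (Section 10.2.6), so early renal events are well covered. The affected outcomes also lie outside the hierarchical testing of the AKI secondary endpoints. All of this limits the weight of the point. It does not resolve the conflict between Section 10.2.9 and footnote h.

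**Conclusion.** The point holds in limited form. For prematurely withdrawn patients, the text no longer requires collection of deaths, admissions and other critical events judged unrelated, contrary to footnote h and to the 6-month rationale in Section 6.3.

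The consequence is possible bias toward noninferiority in the 6-month mortality and morbidity comparisons of Section 12.7.1, chiefly if withdrawal is more frequent in the CECT arm. Under the assumed rates, unequal withdrawal of 12 vs 6 patients moves the upper limit by 0.34 to 0.71 points (5.41 − 5.07 and 5.41 − 4.70). That matters for a result already near 5% and for no other. The documents do not support the stronger reading that every 6-month comparison is biased: they give neither rates nor evidence of differential withdrawal.

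The 48-hour primary endpoint, the AKI secondary endpoints assessed at 48 hours and the sample size are untouched by this route unless withdrawal comes before 48 hours. The change is worth making because it is cheap and the missing outcomes cannot be recovered afterwards.

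**What to change.** - **Section 7.4.1:** separate stopping study visits or procedures from withdrawing consent to follow-up. The investigator's right to withdraw a patient for well-being stays as it is.
- **Section 10.2.9:** delete the shortened period for withdrawn patients. Collect SAEs and critical events to 6 months for every dosed patient unless consent to follow-up is withdrawn, in line with footnote h.
- **Section 9.5:** for patients who have stopped visits but not withdrawn that consent, obtain vital status, RRT and hospitalization at month 6 through the existing Follow-Up 3 telephone contact or from records.
- **Section 12.7.1 or the SAP:** state how patients who still lack 6-month data enter the numerator and denominator, and add a tipping-point sensitivity analysis by arm. Report withdrawals after dosing by arm and reason.

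The cost is protocol wording, one contact or record check for each affected patient, and one added sensitivity analysis. The sample size and the primary analysis do not change.
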